6.4 Follow-up Evaluations

After discontinuation of study treatment, post-study survival status (including post study anticancer therapies) will be collected approximately every 3 months for the first two years and then every six months for the next three years. from the last dose of study treatment. Telephone contact is acceptable.

If patient comes off study treatment prior to progression, continue tumor measurements and radiologic evaluations on schedule until progression or initiation of a subsequent cancer therapy. Toxicity assessments will be continued until resolution or return to baseline. Patients will be followed after last drug dose until toxicity resolution or return to baseline, until progression if patient withdraws before progressive disease, or until study withdrawal if it occurs before this time.

Patients who discontinue study treatment for reasons other than radiographically and/or clinically (i.e., for photographed or palpable lesions) documented disease progression as per RECIST v1.1 definitions will continue to have tumor assessment performed during the follow-up visits every 3 months (± 7 days) from the date of starting protocol therapy until disease progression, initiation of new anticancer therapy or discontinuation of patient from overall study participation (eg, death, patient's request, lost to follow-up), whichever occurs first.

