- e. The end of treatment visit will be performed as soon as possible but no later than 4 weeks (i.e., 28 days) ± 7 days from last dose of investigational product and prior to the initiation of any new anticancer therapy. After discontinuation of study treatment, post-treatment follow-up, including survival status, will be collected every 3 months for the first 2 years and then every 6 months for 3 year for a total of 5 years. Telephone contact is acceptable. If patient comes off study treatment prior to progression, continue tumor measurements and radiologic evaluations on schedule until disease progression or initiation of a subsequent cancer therapy. Toxicity assessments continue until resolution or return to baseline. Patients who discontinue study treatment for reasons other than disease progression should have tumor assessments performed during follow-up visits every 3 months until disease progression, initiation of new anticancer therapy or discontinuation from participation on study.

- f. Due to scheduling, these visits may occur +/- 3 days from the required time point. Additionally, it may be necessary to perform these procedures at unscheduled time points if deemed clinically necessary by the Investigator or in order to accommodate patient/physician scheduling logistics.
- g. Must be performed within 3 days of re-treatment.
- h. Every 4th cycle
- i. Predose and 2-4 hours postdose at investigator's discretion if clinically indicated.
- j. For patients with QTcF ≥ 481 ms at any time, interrupt study treatment and follow the procedures described in the "Ribociclib Dose Modification section". If treatment is resumed, repeat ECGs 7 days and 14 days after dose resumption (and then as clinically indicated). During subsequent cycles, perform predose ECG for every cycle starting at cycle 6, and predose and 2-4 postdose starting at cycle 9 and every 3rd cycle thereafter.

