8.0 Evaluation Criteria

8.1 Antitumor Effect – Solid Tumors

Response and progression will be evaluated in this study using the Response Evaluation Criteria in Solid Tumors (RECIST) guideline (version 1.1) [Eur *J Ca* 45:228-247, 2009]. Changes in the largest diameter (unidimensional measurement) of the tumor lesions and the shortest diameter in the case of malignant lymph nodes are used in the RECIST criteria.

In the present study, tumors will be re-evaluated by CT scan of the chest, abdomen, and pelvis every 12 weeks during treatment and at least 4 weeks after the first observation of a complete or partial response. After discontinuation of protocol treatment, patients who have not progressed will still be re-evaluated every 12 weeks.

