8.1.5 Date of Progression

Date of progression is defined as the first day when the RECIST (version 1.1) criteria for PD are met. CA 125 (GCIG) progression alone is **not** sufficient for progression to be defined.

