8.1.7 Duration of Response

Duration of overall response: The duration of overall response is measured from the time measurement criteria are met for CR or PR (whichever is first recorded) until the first date that recurrent or progressive disease is objectively documented (taking as reference for progressive disease the smallest measurements recorded since the treatment started).

The duration of overall CR is measured from the time measurement criteria are first met for CR until the first date that progressive disease is objectively documented.

Duration of stable disease: Stable disease is measured from the start of the treatment until the criteria for progression are met, taking as reference the smallest measurements recorded since the treatment started, including the baseline measurements.

8.1.8 Progression-free survival: Progression-free survival (PFS) is defined as the duration of time from study entry to time of progression or death or the date of last contact, whichever occurs first.

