9.0 DURATION OF STUDY

- 9.1 In the absence of treatment delays due to adverse event(s), treatment may continue until one of the following criteria applies:
 - Disease progression,
 - Intercurrent illness that prevents further administration of treatment,
 - Unacceptable adverse event(s),
 - Patient withdraws consent for the study,
 - Patient non-compliance with the protocol,
 - Death,
 - Pregnancy, or
 - General or specific changes in the patient's condition render the patient unacceptable for further treatment in the judgment of the investigator.
 - 9.1.1 If patient comes off study treatment prior to progression, continue tumor measurements and radiologic evaluations on schedule until progression or initiation of a subsequent cancer therapy. Toxicity assessments will be continued until resolution or return to baseline. Patients will be followed after last drug dose until toxicity resolution or return to baseline, until progression if patient withdraws before progressive disease, or until study withdrawal if it occurs before this time.
 - 9.1.2 All patients will be treated (with completion of all required case report forms) until disease progression or study withdrawal. Patients will then be followed every three months for the first two years and then every six months for the next three years. Patients will be monitored for delayed toxicity and survival for this 5-year period with Follow-Up Forms submitted to the GOG Statistical and

Data Center, unless consent is withdrawn. Follow-Up Forms will no longer be required if the study is terminated prior to the completion of the 5-year follow-up period.

9.1.3 A patient is considered off study therapy when the patient has progressed or died, a non-protocol drug or therapy (directed at the disease) is initiated or all study therapy is totally discontinued. Report all treatment received on Cycle Drug Information Forms and adverse events on Adverse Event Forms up until the patient qualifies as being off study therapy.

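### PFS runs to last contact, but scheduled scans may stop at new anticancer therapy; patients who switch without documented progression then count as progression-free, which raises PFS on average

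*Combined protocol and SAP*

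**What the plan says.** - **PFS definition (8.1.8):** time runs "from study entry to time of progression or death or the date of last contact, whichever occurs first". Section 11.4 adds only Kaplan-Meier medians and graphs. Neither section deals with new anticancer therapy or with the last evaluable scan.
- **What counts as progression (8.1.5):** "Date of progression is defined as the first day when the RECIST (version 1.1) criteria for PD are met". CA-125 alone does not count.
- **Scans after treatment stops, three places with a stop:** section 6.4 has sites "continue tumor measurements and radiologic evaluations on schedule until progression or initiation of a subsequent cancer therapy"; 9.1.1 repeats this, and 6.5 footnote e runs scans "until disease progression or initiation of a subsequent cancer therapy".
- **Scans after treatment stops, two places without a stop:** sections 8.1 and 8.1.4 both state: "After discontinuation of protocol treatment, patients who have not progressed will still be re-evaluated every 12 weeks".
- **Contact after treatment stops (6.4):** "post-study survival status (including post study anticancer therapies) will be collected approximately every 3 months for the first two years", then every six months for three more years. "Telephone contact is acceptable".
- **Switching before progression is foreseen:** 9.1.3 takes a patient off study therapy on progression or death, and separately when "a non-protocol drug or therapy (directed at the disease) is initiated". Section 8.1.3.4 describes symptomatic deterioration without objective progression and asks for efforts to document progression afterwards.

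**The concern.** Last contact is a sound censoring date for overall survival, because a telephone call establishes vital status. It is not sound for PFS, because a call cannot show that RECIST progression is absent. If the scan stop in 6.4, 6.5 and 9.1.1 is followed, a patient who starts another therapy without documented progression stays in the PFS risk set, possibly for years. In that time death is the only event with a planned means of detection. Progression found by chance may still be recorded, but no visit is scheduled to look for it.

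At stake is a secondary endpoint in a single-arm trial. There is no control arm to share the bias, and a confidence interval does not show it.

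**Working it through.** **1. The plan's own figures.** The documents give no sample size, event count or target for PFS, so there is no PFS figure to reproduce. The stated operating characteristics belong to the two-stage response design. Averaged over 19-26 and 44-51 patients with the limits in 11.3, exact binomial calculation gives 0.636 early termination, 0.0988 type I error and 0.900 power, against the stated 64%, 10% and 90%. None of these uses PFS.

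**2. Direction.** Under the stated rule with a scan stop, a switcher's event is death. With full scanning it is the earlier of the scan showing progression and death. Each recorded event time is therefore equal or later, and the curve being estimated is equal or higher.

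**3. Size: inputs.** The switch share q is not in the documents; 10% and 20% are assumed. True median time to progression is 12 months (assumed), or 7.4 months, the hormonal-therapy figure in section 1.2. Scans are every 12 weeks (2.76 months). Contact lasts 60 months. Median post-progression survival (PPS) is 3, 6 or 36 months (assumed). Times are exponential, and no progression is recorded after a switch, so the sizes are upper bounds for each scenario.

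**4. Hand check, switching just before progression.** The rise at 24 months is q × [OS(24) − PFS(24)].
- Median 12, PPS 36: the hazards are ln2/12 = 0.0578 and ln2/36 = 0.0193. The last scan before month 24 is at 8 × 2.76 = 22.08 months, so PFS(24) is about exp(−0.0578 × 22.08) = 27.9%. OS(24) = (0.0578 × 0.630 − 0.0193 × 0.250)/(0.0578 − 0.0193) = 82%. The rise is 0.20 × (82 − 27.9) = 10.8 points.
- Median 12, PPS 3: OS(24) is 33.2% and PFS(24) is 27.4%. The rise is 0.20 × 5.8 = 1.2 points.
- Median 7.4, PPS 36: OS(24) is 76.6% and PFS(24) is 12.6%. The rise is 0.20 × 64.0 = 12.8 points. With PPS 3 it is about 1 point.

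**5. Simulation (400,000 patients per scenario, median 12).** 24-month PFS in %:

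| Switching | q | PPS | Full scanning | As written | Last-scan censoring | New therapy as event |
|---|---|---|---|---|---|---|
| Unrelated to progression | 10% | 3 | 27.3 | 27.9 | 27.0 | 23.5 |
| | 10% | 6 | 27.7 | 29.0 | 27.3 | 23.7 |
| | 10% | 36 | 27.8 | 31.0 | 27.5 | 23.8 |
| | 20% | 3 | 27.4 | 28.7 | 26.7 | 19.4 |
| | 20% | 6 | 27.8 | 30.5 | 27.1 | 19.7 |
| | 20% | 36 | 27.8 | 34.6 | 27.1 | 19.7 |
| Just before progression | 10% | 3 | 27.4 | 28.0 | 30.9 | 27.1 |
| | 10% | 6 | 27.5 | 29.2 | 31.1 | 27.3 |
| | 10% | 36 | 27.9 | 33.4 | 31.5 | 27.7 |
| | 20% | 3 | 27.4 | 28.6 | 34.9 | 26.9 |
| | 20% | 6 | 27.6 | 30.8 | 35.2 | 27.1 |
| | 20% | 36 | 28.0 | 38.8 | 35.5 | 27.4 |

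With a median of 7.4 months, q = 20% and PPS 36, full scanning gives 12.6%. The stated rule gives 23.2% (unrelated) or 25.4% (just before progression).

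**6. Against sampling error.** With 48 patients the SD of 24-month PFS is about √(0.274 × 0.726/48) = 6.4 points. At a median of 12, only the 20%, PPS 36 cases exceed it.

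**7. The median, which is what 11.4 names.** In large samples at a true median of 12, the full-scan median is 13.8 months, because progression is dated at scans. The stated rule leaves it at about that value except with 20% switching just before progression and PPS 36 (16.6 months). In trials of 48 with PPS 6 or 36 it is unchanged in 56-82% (unrelated) or 17-63% (just before progression).

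**8. Staggered follow-up.** With 48 patients, 17 months of accrual, 24 months of further follow-up, 20% unrelated switching and PPS 6, the as-written curve dips below full scanning somewhere in about 30% of trials. With 5 months of further follow-up the median is lower in about 2%. A delayed death falls in a thinner risk set and takes a larger step.

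**The case against.** - **The scan texts may not conflict.** Sections 8.1 and 8.1.4 are general statements of frequency and silent on new therapy; the other three are specific and agree with each other. A reader might infer a flat contradiction. The documents support less: an unqualified instruction beside a qualified one, which sites could apply differently. Sections 6.4 and 9.1.1 also follow patients to progression if they withdraw before it. The need to reconcile the texts stands.
- **The bias is not strictly one-way.** A reader might infer that the stated rule can only raise PFS. That is true of the curve being estimated, but not of every small-sample curve under the staggered accrual in 11.2 (step 8). Upward on average is the supportable statement.
- **The sizes are for a statistic the plan does not name.** Section 11.4 promises medians and graphs, not 24-month PFS, and the median often stays put. The synopsis expects a 22-month protocol, 9.1.2 lets follow-up end early, and no PFS cut-off is stated, so 60 months of contact may be generous. This limits the practical effect, but the graph is still distorted.
- **The usual remedy can be worse.** Last-scan censoring discards deaths after a switch. With 20% switching just before progression and PPS 6 it gives about 35%, against 31% as written and 28% with full scanning. It is the more optimistic rule when PPS is below about 14-16 months. This stands, and is why it should not be adopted alone.
- **The two alternative curves do not bound the truth.** When switching is unrelated to progression, both lie below full scanning (26.7% and 19.4% against 27.4% at 20%, PPS 3).

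**Conclusion.** The concern holds on a condition: if scans stop at new therapy, the last-contact rule biases PFS upward on average. If scans continue as 8.1 and 8.1.4 can be read, the problem largely disappears. Confidence is high on the wording, the need to reconcile and the average direction.

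The size cannot be fixed from the documents. It is nil with no switching. At an assumed 20%, 24-month PFS rises by about 1 to 11 points (true median 12 months) or 1 to 13 points (7.4 months), depending on survival after progression and on why patients switch. Long survival is plausible, since section 1.1 cites a median OS of 101.7 months, but that figure is not post-progression survival in recurrent disease.

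A reader might infer that the trial's conclusion is at risk. It is not: PFS carries no test or threshold, and the response decision does not use it. The point should be corrected because the stated rule is wrong for PFS and the correction is cheap.

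**What to change.** 1. **Scan rule.** Reconcile 8.1 and 8.1.4 with 6.4, 6.5 footnote e and 9.1.1, so that all five say the same about scans after new anticancer therapy.
2. **Censoring (8.1.8).** Censor patients alive without RECIST progression at their last adequate tumor assessment, and keep last contact for OS only (8.1.9). If scans stop at new therapy, censor switchers at the last adequate assessment before it started. If scans continue, count later progression and death as events.
3. **Sensitivity analysis (11.4), if scans stop.** Require a Kaplan-Meier curve that counts new anticancer therapy as a PFS event, shown beside the main curve, with the number who switched without documented progression. Present the pair as showing dependence on the rule, not as bounds.
4. **Data.** Section 6.4 collects post-study anticancer therapies but does not say that start dates are captured. Confirm or add that field.

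The cost is wording in a few sections, one extra curve and possibly one data field. The downsides are more censoring and the loss of deaths after a switch under last-scan censoring, which is why item 3 should be required rather than optional.

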8.1.9 Overall Survival

Overall survival is defined as the time from study entry to time of death or date of last contact.

9.0 DURATION OF STUDY

- 9.1 In the absence of treatment delays due to adverse event(s), treatment may continue until one of the following criteria applies:
 - Disease progression,
 - Intercurrent illness that prevents further administration of treatment,
 - Unacceptable adverse event(s),
 - Patient withdraws consent for the study,
 - Patient non-compliance with the protocol,
 - Death,
 - Pregnancy, or
 - General or specific changes in the patient's condition render the patient unacceptable for further treatment in the judgment of the investigator.
 - 9.1.1 If patient comes off study treatment prior to progression, continue tumor measurements and radiologic evaluations on schedule until progression or initiation of a subsequent cancer therapy. Toxicity assessments will be continued until resolution or return to baseline. Patients will be followed after last drug dose until toxicity resolution or return to baseline, until progression if patient withdraws before progressive disease, or until study withdrawal if it occurs before this time.
 - 9.1.2 All patients will be treated (with completion of all required case report forms) until disease progression or study withdrawal. Patients will then be followed every three months for the first two years and then every six months for the next three years. Patients will be monitored for delayed toxicity and survival for this 5-year period with Follow-Up Forms submitted to the GOG Statistical and

Data Center, unless consent is withdrawn. Follow-Up Forms will no longer be required if the study is terminated prior to the completion of the 5-year follow-up period.

9.1.3 A patient is considered off study therapy when the patient has progressed or died, a non-protocol drug or therapy (directed at the disease) is initiated or all study therapy is totally discontinued. Report all treatment received on Cycle Drug Information Forms and adverse events on Adverse Event Forms up until the patient qualifies as being off study therapy.

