6.2 Evaluations on Treatment

Collection of Concomitant Medications and Adverse Events (AEs) should occur throughout the study, as described. Pre-treatment (Screening) evaluations do not need to be repeated if within 28 days of Cycle 1 Day 1.

Day 1 (±3 days)

- History and physical exam with vital signs
- Labs: CMP, CPK, CBC with differential (diff), Uric acid, Urinalysis
- If WOCBP, pregnancy test within 3 days of treatment for Cycle 1 only
- AEs

- ECG (if clinically indicated)
- Study drugs to be taken daily at the same time every day for 21-consecutive days.
- CA-125
- Lipid panel (total cholesterol, HDL, LDL, triglycerides) fasting preferred
- Coagulation (PT and INR)

Day 21 (±3 days)

- Ribociclib –start of 1-week off period.
- Letrozole Continue taking through the week off period of Ribociclib.
- 6.3 Off-Treatment Evaluations (End of Treatment or EOT visit)

The end of treatment visit will be performed as soon as possible but no later than 4 weeks (i.e., 28 days) $\pm 7 \text{ days}$ from last dose of investigational product and prior to the initiation of any new anticancer therapy.

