Information regarding AEs and SAEs will be collected from the time of informed consent until 30 days from the last dose administered.

When possible, adverse events should be described in terms of a change in the baseline status or with a diagnosis or summary term rather than as individual symptoms. The Investigator is responsible for reporting SAEs to the appropriate Institutional Review Board (IRB) or other committees in accordance with local institutional and IRB policies.

10.1.3 Criteria for Determining Adverse Event Severity:

The descriptions and grading scales found in the revised NCI Common Terminology Criteria for Adverse Events (CTCAE) version 5.0 will be utilized for AE reporting.

10.1.4 Criteria for Determining Adverse Event Causality:

The following attribution categories will be used in assessing the relationship between the AE and the study drug:

RELATIONSHIP	ATTRIBUTION	DESCRIPTION
Unrelated to investigational	Unrelated	The AE is clearly NOT related to the intervention
agent/intervention	Unlikely	The AE is doubtfully related to the intervention
Related to investigational	Possible	The AE may be related to the intervention
agent/intervention	Probable	The AE is likely related to the intervention
	Definite	The AE is clearly related to the intervention

10.1.5 SAE Reporting to GOG and Novartis:

The investigator must report to GOG any serious adverse event, whether or not considered drug-related, within 24 hours of any site personnel becoming aware of the event. Please see the Data Management Manual for instructions for submitting SAE reports to GOG in Medidata Rave.

The GOG Regulatory Compliance Department will forward all SAE reports to Novartis within 24 hours of first awareness.

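### Section 9.1.3 ends Adverse Event Form entry at off-therapy status while 10.1.2 collects adverse events to 30 days after the last dose, so new non-serious events in between may be recorded at some sites only

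*Combined protocol and SAP*

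**What the plan says.** Section 9.1.3 (Duration of Study) defines off-therapy status and ties form completion to it. It begins "A patient is considered off study therapy when the patient has progressed or died", then adds the start of a non-protocol treatment directed at the disease, and closes with the case where "all study therapy is totally discontinued". Sites complete Cycle Drug Information Forms and report "adverse events on Adverse Event Forms up until the patient qualifies as being off study therapy".

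Section 10.1.2 (GOG Reporting Requirements) sets a different end point: "Information regarding AEs and SAEs will be collected from the time of informed consent until 30 days from the last dose administered".

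Other provisions deal with toxicity after treatment:

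- Section 9.1.1: "Toxicity assessments will be continued until resolution or return to baseline". Section 6.4 and footnote e of the Schedule of Assessments say the same.
- Section 9.1.2: "Patients will be monitored for delayed toxicity and survival for this 5-year period with Follow-Up Forms".
- Section 6.2: "Collection of Concomitant Medications and Adverse Events (AEs) should occur throughout the study, as described". The Schedule marks AE assessment as continuous.
- Section 10.1.5: SAEs are reported within 24 hours of site awareness, with no reference to off-therapy status.

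Frequency and severity of AEs is a secondary endpoint (11.1.2). Section 11.4 tabulates the frequency and maximum grade of acute AEs. It does not define acute, state an observation window or name a source form.

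**The concern.** Sites have two instructions with different end points for the same data. A site that follows 9.1.3 closes the AE Form at off-therapy status. A site that follows 10.1.2 carries on for 30 days after the last dose. Both would be complying with the protocol.

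The trial is small and single-arm, with 19 to 51 patients expected across 25 centers, and its toxicity table is a secondary result. If centers use different windows, that table mixes two observation periods without saying so. The reported frequencies and maximum grades would then depend partly on which section a center read.

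**Working it through.** The plan gives no figure to reproduce here. The check sets the provisions side by side and then follows individual events through them.

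**1. Stop points and forms**

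| Provision | Covers | Stops at | Form named |
|---|---|---|---|
| 9.1.3 | AEs | Off-therapy status | Adverse Event Form |
| 10.1.2 | AEs and SAEs | 30 days after last dose | None |
| 9.1.1, 6.4, Schedule footnote e | Toxicity assessments | Resolution or return to baseline | None |
| 9.1.2 | Delayed toxicity, survival | 5 years | Follow-Up Forms |
| 6.2, Schedule AE row | AE collection | No stop date given | None |
| 10.1.5 | SAEs | Not tied to off-therapy status | SAE report in Rave |
| 11.4 | Acute AE table | No window given | None |

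No text ranks 9.1.3 against 10.1.2 or assigns a form to the 30 days.

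**2. Four events followed through the text**

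- *An AE that starts on therapy and leads to stopping.* It is reportable under 9.1.3 because it arose on therapy, and 9.1.1 then follows it to resolution. No gap.
- *An SAE on day 20 after the last dose.* It is reported under 10.1.5. No gap.
- *A new non-serious AE on day 20 after the last dose.* It falls inside the 10.1.2 window and outside 9.1.3. The text in 9.1.1 concerns resolution, so it reads as follow-up of toxicity already present. The text in 9.1.2 concerns delayed toxicity on another form, collected three-monthly at first, and nothing links that form to the table in 11.4. **Gap.**
- *A new non-serious AE between the progression date and a later last dose, if any dose is taken in that interval.* Progression alone confers off-therapy status, so 9.1.3 has closed the form although dosing continues. **Gap.**

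The third case can readily arise. The Schedule marks hematology, chemistry with liver tests, coagulation and urinalysis at End of Treatment. That visit is due no later than 28 ± 7 days after the last dose, normally after off-therapy status begins. Read literally, 9.1.3 lets a new abnormality found there go unentered on an AE Form. The visit can also fall as late as day 28 + 7 = 35, which is 5 days beyond the 10.1.2 window.

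**3. Calendar time in dispute**

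Assume that every patient goes off therapy at the last dose and is followed for the full 30 days:

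- Target accrual: 48 × 30 = 1,440 patient-days.
- Permitted final range, 44 to 51: 44 × 30 = 1,320 to 51 × 30 = 1,530.
- Stopping at stage 1, 19 to 26: 19 × 30 = 570 to 26 × 30 = 780.

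These totals also suppose that every site follows 9.1.3. Deaths and sites that follow 10.1.2 reduce them. Doses taken after the progression date increase them. They measure observation time, not events.

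**4. Direction**

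Omitting an event can leave a frequency or a patient's maximum grade unchanged, or lower it. It cannot raise either.

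**The case against.** The strongest defense is that the sections divide the work. On this reading, 9.1.3 names the form for the on-therapy period, 9.1.2 names Follow-Up Forms for what comes after, and 10.1.2 states only that information is collected. In addition, 10.1.2 sits under the heading for adverse event reporting, so sites may well follow it. Section 10.2 sends sites to a Data Management Form Manual for the forms, and that manual, which is not among the documents reviewed, may settle the question. The analysis is descriptive and has one arm, so no treatment comparison can be biased.

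Much of this stands, and it limits the point to new non-serious events. It does not remove the conflict. The protocol does not state the division between forms, does not connect Follow-Up Forms to the acute-AE table, and should not depend on a manual to resolve a contradiction in its own text.

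A reader might draw three stronger conclusions that the documents do not support:

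- *Post-treatment toxicity information is lost.* Sections 9.1.1, 9.1.2, 6.4 and 10.1.5 all provide for it in part.
- *About 12% of AE data is missing.* The arithmetic would be 7.4 months × 30.4 = 225 days on treatment, then 30 / (225 + 30) = 0.12. But 7.4 months is the median progression-free survival that Section 1.2 cites for hormonal therapies, not treatment duration on this combination. The result is also a share of calendar time, whereas 11.4 tabulates frequency and maximum grade.
- *Patients who stop for toxicity lose their events.* Section 1.8 cites AE discontinuation of 8.1% and 16.8% on the combination in the phase III breast cancer trial. Those AEs led to stopping, so they arose on therapy and are reportable even under 9.1.3. The documents give no rate of events first arising after the last dose.

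**Conclusion.** The two stop points conflict and the protocol does not say which governs. The consequence is limited: new non-serious AEs arising after off-therapy status, including laboratory abnormalities at the End of Treatment visit, may be absent from AE Forms at some sites. Any effect on the secondary toxicity table is toward lower frequencies and maximum grades, or none.

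The size in events cannot be estimated. It depends on how many sites follow 9.1.3 and how many such events occur, and the documents give neither. The conclusion also assumes that the 11.4 table draws on AE Forms, which is likely but not stated.

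The primary response endpoint and the stage 1 and stage 2 decision rules use no AE data. The DLT review has its own definition, covering the first 28 days of treatment, and does not rest on the post-treatment window. This is an inconsistency worth correcting, not a threat to the trial's main conclusion.

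**What to change.** 1. Amend 9.1.3 so that Adverse Event Forms are completed through the window already set in 10.1.2, consent to 30 days after the last dose, with a cross-reference. State whether the last dose means the later of the two study drugs.
2. Keep off-therapy status as the cut-off for Cycle Drug Information Forms only.
3. State in 11.4 that the toxicity table covers this same window and is built from the AE Forms.
4. Say how a new finding is recorded when the End of Treatment visit falls on days 31 to 35.

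The cost is a few sentences of protocol text and slightly more AE data entry at sites. Reported AE rates may be slightly higher. No sample size, decision rule or treatment instruction changes.
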